6.2. Analysis of Primary Endpoint

6.2.1. DLT (Part 1)

Dose Limiting Toxicity is the primary endpoint of the dose escalation phase of the study, which will be summarized by dose level using the Per Protocol Analysis Set for patients in the dose escalation portion of the study. A listing of the DLTs will also be provided. If necessary, a summary and listing of the DLT by malignancy may be provided using the Per Protocol Analysis Set for patients in the MTD expansion portion of the study.

6.2.2. Safety Endpoints (Part 1 and Part 2)

In safety data tabulations, only data collected during the on-treatment period, defined as on or after the first dose of study treatment, and before the last dose of study treatment + 28 days, or the start of any other anti-cancer therapy, whichever is earlier, will be included. In safety data listings, all collected data will be listed.

Adverse Events

Adverse Events (AEs) will be graded by the investigator according to the CTCAE version 4.03 and coded using the MedDRA.⁴ The focus of AE summaries will be on Treatment Emergent Adverse Events, those with initial onset or increasing in severity after the first dose of study medication. The number and percentage of patients who experienced any AE, serious AE (SAE), treatment related AE, and treatment related SAE will be summarized according to worst toxicity grades. The summaries will present AEs both on the entire study period and by cycle (Cycle 1 and Cycles beyond 1) for overall and each dose. The Safety Analysis Set will be used. Part 1 and Part 2 data will be summarized separately and will also be pooled together for analysis. Pfizer standard on safety data reporting will be followed.

Laboratory Tests Abnormalities

The number and percentage of patients who experienced laboratory test abnormalities will be summarized according to worst toxicity grade observed for each laboratory test for overall and each dose. The analyses will summarize laboratory tests both in the entire study period and by cycle (Cycle 1 and Cycles beyond 1). Shift tables will be provided to examine the distribution of laboratory abnormalities. The Safety Analysis Set will be used.

For laboratory tests without CTC grade definitions, results will be categorized as normal, abnormal high/low or not done.

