- v. **AE Assessments:** Adverse events should be documented and recorded at each visit using NCI CTCAE version 4.03. AEs (serious and non-serious) should be recorded on the CRF from the time the patient has taken at least 1 dose of investigational product. Patients must be followed for AEs for 28 days after the last treatment administration or until all drug related toxicities have resolved, whichever is later; or earlier than 28 days should the patient commence another anticancer therapy in the meantime. Additional, irAEs will be collected with a follow up phone call at 90 and 120 days after last dose administration date to collect post treatment related AE information.
- w. **SAE Assessments:** For SAEs, the active reporting period to Pfizer or its designated representative begins from the time that the patient provides informed consent, which is obtained prior to the patient's participation in the study, ie, prior to undergoing any study related procedure and/or receiving investigational product, through and including 150 calendar days after the last administration of the investigational product or until administration of subsequent anti-cancer therapy whichever comes first. SAEs occurring to a patient after the active reporting period has ended should be reported to the sponsor if the investigator becomes aware of them; at a minimum, all SAEs that the investigator believes have at least a reasonable possibility of being related to investigational product are to be reported to the sponsor.
- x. **Concomitant Medications and Non Drug Supportive Interventions:** all concomitant medications should be recorded in the CRF including supportive care drugs (eg, Anti-emetic treatment and prophylaxis), drugs used to treat adverse events or chronic diseases, and non-drug supportive interventions (eg, transfusions).
- y. **Subsequent anticancer therapy:** After the completion of the EOT visit subsequent anti-cancer therapy will be documented and recorded for patients who discontinue investigational products and continue in 120 day safety follow-up, and subsequently during survival follow-up.

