6.4. Follow-up for Late Immune-related Adverse Events

Patients will undergo telephone follow-ups at 90 and 120 day (± 7 days) after the last dose of study drug to assess potential late irAEs. If any concern arises, patient will be called in for an inpatient follow up visit within 5 calendar days of initial phone call. For this inpatient follow-up visit, the [Schedule Of Activities](#) will be similar to the 1-month follow-up visit completed after EOT.

Patients continuing to experience late immune-related toxicity at this point (up to 120 days after last dose of study drug) will continue to be followed at least every 4 weeks until resolution or determination, in the clinical judgment of the investigator, that no further improvement is expected.

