6.6. Patient Withdrawal

The reason for a patient's discontinuation from treatment will be documented in the end of study/withdrawal CRF. Patients will be followed for at least 120 days after the last dose of study drug for AEs.

Patients may withdraw from treatment at any time at their own request, or they may be withdrawn at the discretion of the investigator or sponsor for safety or behavioral reasons, or the inability of the patient to comply with the protocol-required schedule of study visits or procedures at a given study site.

Reasons for withdrawal of study treatment may include:

- Objective disease progression;*
- Global deterioration of health status requiring discontinuation;
- Unacceptable toxicity;
- Pregnancy;
- Significant protocol violation;
- Lost to follow-up;
- Patient refused further treatment;
- Study terminated by sponsor;
- Death.

*In the case of radiological progression but in the absence of clinical deterioration, if investigator deems it to be in the patient's best interests, the patient will be allowed to stay on study.

Reasons for withdrawal from study follow-up may include:

- Completed study follow-up;
- Study terminated by sponsor;
- Lost to follow-up;
- Refused further follow-up;
- Death.

If a patient does not return for a scheduled visit, every effort should be made to contact the patient. All attempts to contact the patient and information received during contact attempts must be documented in the patient's medical record. In any circumstance, every effort should be made to document patient outcome, if possible. The investigator should enquire about the reason for withdrawal, request the patient to return for a final visit, if applicable, and follow-up with the patient regarding any unresolved AEs.

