8.2. Reporting Period

For SAEs, the active reporting period to Pfizer or its designated representative begins from the time that the patient provides informed consent, which is obtained prior to the patient's participation in the study, ie, prior to undergoing any study-related procedure and/or receiving investigational product, through and including 150 calendar days after the last administration of the investigational product or until administration of subsequent anti-cancer therapy whichever comes first. Death must be reported as an SAE if it occurs within 150 calendar days after last administration of the investigational product, irrespective of any intervening treatment. SAEs occurring to a patient after the active reporting period has ended should be reported to the sponsor if the investigator becomes aware of them. At a minimum, all SAEs that the investigator believes have at least a reasonable possibility of being related to investigational product are to be reported to the sponsor.

If an SAE occurs after informed consent is signed and before study drug is administered, this information will be reported on an SAE Form and will be recorded in the safety database.

AEs (serious and non-serious) should be recorded on the CRF from the time the patient has taken at least 1 dose of investigational product through the patient's last visit. Patients must be followed for AEs for 28 days after the last treatment administration or until all drug related toxicities have resolved, whichever is later; or earlier than 28 days should the patient commence another anticancer therapy in the meantime. Additional, immune-related AEs will be collected with a follow-up phone call at 90 and 120 days after last dose administration date to collect post-treatment related AE information.

If a patient begins a new anticancer therapy, the AE reporting period for non-serious AEs ends at the time the new treatment is started.

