9.6.2. Analysis of Secondary Safety Endpoints

Adverse Events

Adverse Events as characterized by type, frequency, severity, timing, seriousness, and relationship to study therapy PF-06801591 will be tabulated.

Adverse Events will be graded by the investigator according to the NCI CTCAE version 4.03, and coded using the Medical Dictionary for Regulatory Activities. The focus of AE summaries will be on treatment emergent AEs, those with initial onset or increasing in severity after the first dose of study treatment. The number and percentage of patients who experienced any AE, SAE, treatment-related AE, and treatment related SAE will be summarized according to worst toxicity grades. The summaries will present AEs both on the entire study period and by cycle (Cycle 1 and Cycles beyond 1).

Laboratory Test Abnormalities

Laboratory abnormalities as characterized by type, frequency, severity (as graded by NCI CTCAE version 4.03), and timing will be summarized by treatment group. Baseline corrected QTcF interval at the maximum plasma concentration at steady state at the MTD will be tabulated by treatment group. Central assessment of the QTcF interval would be considered primary but listings will be produced for the local (study site) assessment as well.

The number and percentage of patients who experienced laboratory test abnormalities will be summarized according to worst toxicity grade observed for each laboratory assay. The analyses will summarize laboratory tests both on the entire study period and by cycle (Cycle 1 and Cycles beyond 1). Shift tables will be provided to examine the distribution of laboratory toxicities.

For laboratory tests without CTCAE grade definitions, results will be categorized as normal, abnormal, or not done.

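### SAP 6.2.2 leaves Part 2 AEs and SAEs that start 28 or more days after the last dose out of its safety counts, although the protocol collects immune-related AEs to day 120 and SAEs to day 150

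*SAP*

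**What the plan says.** SAP 6.2.2 covers safety in both parts. It admits to the tabulations only data from the first dose onward and "before the last dose of study treatment + 28 days, or the start of any other anti-cancer therapy, whichever is earlier, will be included". Everything else appears in listings, which have no time limit. The AE outputs it names are these: "The number and percentage of patients who experienced any AE, serious AE (SAE), treatment related AE, and treatment related SAE will be summarized" by worst toxicity grade. Laboratory abnormalities are tabulated under the same rule.

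The protocol's collection windows are longer.

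- **Immune-related AEs.** The Part 2 Schedule of Activities (footnote v) states that "irAEs will be collected with a follow up phone call at 90 and 120 days after last dose administration date". Protocol 6.4 gives the purpose of these calls, made at 90 and 120 days (±7): they take place "after the last dose of study drug to assess potential late irAEs".
- **SAEs.** Protocol 8.2 runs active reporting through day 150 after the last administration, or to subsequent anti-cancer therapy if that comes first.
- **Deaths.** Protocol 8.2 also says: "Death must be reported as an SAE if it occurs within 150 calendar days after last administration of the investigational product". Starting another therapy does not lift this requirement.
- **Non-serious AEs.** Another anti-cancer therapy closes this window: "the AE reporting period for non-serious AEs ends at the time the new treatment is started" (Protocol 8.2).

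On reporting, Protocol 9.6.2 says: "The summaries will present AEs both on the entire study period and by cycle". It sets no 28-day limit. SAP 6.2.2 repeats that sentence beneath its 28-day rule.

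**The concern.** AE frequency, timing and seriousness are primary endpoints of Part 2 (Protocol 2.2). The day-90 and day-120 calls exist to find late immune-related AEs. Under the SAP as written, a Part 2 event first seen at one of those calls, with onset on or after day 28, enters no numerator in 6.2.2. The same holds for an SAE starting between day 28 and day 150. A reader who wanted a rate would have to count from listings and construct a denominator.

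The cut can also fall on patients with toxicity. Protocol 5.4.3.1 allows a persistent Grade 2–3 drug-related AE up to 12 weeks after the last dose to recover before treatment is discontinued. For a patient who never resumes, the tabulation window closes at day 28 of that hold.

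At stake is how fully the report can describe late toxicity of the subcutaneous regimen. The validity of the on-treatment tables is not in question.

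**Working it through.** The plan states no figure to reproduce, so the check compares windows. I take the tabulation rule to apply to the date of onset.

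**Step 1. Windows, in days after the last dose.**

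| Data | Collected to | Tabulated to | Maximum days collected but not tabulated |
|---|---|---|---|
| Immune-related AEs (Protocol 6.4, 8.2) | 120 (nominal) | before 28 | 120 − 28 = 92 |
| SAEs (Protocol 8.2) | 150, or new therapy | before 28, or new therapy | 150 − 28 = 122 |
| Deaths reported as SAEs (Protocol 8.2) | 150, regardless of new therapy | before 28, or new therapy | 150 − 28 = 122, and longer where new therapy starts before day 28 |

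As shares of post-dose follow-up these are 92/120 = 77% and 122/150 = 81%. They are maxima. SAE collection stops at new therapy, and so does non-serious AE reporting.

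**Step 2. Can the late calls feed the tables?** The earliest permitted call is day 90 − 7 = 83. Any event with onset on or after day 28 that is first reported at a call is outside the window.

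**Step 3. Where do the late events appear?**

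- SAP 6.2.2 counts: no.
- SAP 6.2.2 listings: yes.
- Overall survival (SAP 3.2 and 6.3.1): Part 2 deaths at any time, measured from treatment start, with no count by time since last dose.
- Late immune-related dose-limiting toxicities (SAP 2.2.1): these feed the Part 1 mTPI decisions only.

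**Step 4. Size.** The documents give no late-event rate. Purely as an illustration, let p be an assumed proportion of patients with a first immune-related AE 28 or more days after the last dose, and n the number still under collection. The expected number omitted is n × p, and the chance of at least one is 1 − (1 − p)^n.

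| p | n = 100: expected; chance of at least one | n = 50: expected; chance of at least one |
|---|---|---|
| 1% | 1; 63% | 0.5; 40% |
| 2% | 2; 87% | 1; 64% |
| 5% | 5; 99% | 2.5; 92% |

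Here n = 100 is the whole of Part 2 and so an upper bound. Treatment may last 2 years and the trial ends 2 years after the last patient's first dose, so late enrollees who complete treatment may have little post-treatment follow-up. The n = 50 column supposes that half have left collection through new therapy.

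**The case against.** The strongest defence is that the SAP window matches the period in which all AEs are sought. Protocol 8.2 follows AEs for 28 days after the last dose, longer for unresolved drug-related toxicity and less if new therapy starts. After that, collection narrows to immune-related AEs by telephone and to SAEs. A rate over the longer period would mix complete and selective ascertainment. This stands, and is why the 28-day tables should remain the main display. Protocol 6.6 is broader ("Patients will be followed for at least 120 days after the last dose of study drug for AEs"), but it does not sit easily with 8.2, and the point does not depend on it.

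Other parts of the defence also stand. Late events are listed. Part 2 deaths are largely covered by overall survival, which makes deaths the weakest element. SAP 6.2.2 also says the sponsor's safety reporting standard will be followed. That standard is not among the documents, so it may supply further tables.

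A reader might infer more than the text supports:

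- **That the cut governs all safety output.** It does not. Dose-limiting toxicities are summarised under SAP 6.2.1, outside this rule, and delayed events during continued dosing are tabulated normally.
- **That the cut is why no immune-related AE or death table exists.** SAP 6.2.2 names neither table for any period. The rule removes late events from the any-AE, SAE and treatment-related counts; a dedicated immune-related table would be a new output.
- **That the sentence on the whole study period leaves the tables open to two constructions.** The on-treatment restriction opens the section and has no exception. The phrase is set against a by-cycle split, so it most naturally means all cycles combined. The wording merits tidying, but nothing shows that different primary tables would result.

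**Conclusion.** The point holds in a limited form. As SAP 6.2.2 is written, Part 2 AEs and SAEs with onset 28 or more days after the last dose are excluded from the counts it names, and nothing else in that section counts them. Deaths after new anti-cancer therapy are excluded too, although the protocol reports them to day 150 regardless.

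The affected collection time is at most 92 days for immune-related AEs and 122 days for SAEs. The number of patients affected cannot be estimated from the documents. The conclusion assumes that onset date decides inclusion, and it is confined to what the SAP names, since the sponsor standard cannot be seen. This is a worthwhile, inexpensive improvement in reporting; it does not invalidate the planned tables.

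**What to change.** Keep the 28-day tables as the main safety display. Add to SAP 6.2.2, by part and pooled:

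- (a) a supplementary table of investigator-attributed immune-related AEs by worst grade, from first dose to 120 days after the last dose. The case report form already records this attribution (Protocol 8.1).
- (b) a supplementary table of SAEs to 150 days after the last dose, with deaths to day 150 not truncated at new anti-cancer therapy. Show disease-progression deaths separately, because Protocol 8.6 records a fatal progression within the reporting period as a Grade 5 SAE.

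Footnote both: collection after day 28 is selective and largely stops at new therapy, so late rates may undercount.

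As a minor clean-up, state in SAP 6.2.2 that the whole-study AE summary means all cycles combined within the on-treatment window, and note that this narrows Protocol 9.6.2. The SAP is allowed to modify the protocol's plans, but the change should be visible.

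The cost is two supplementary tables, a footnote and a short clarification, all from data already collected. The downside is the risk that readers take incomplete late rates as complete, which the footnote is there to prevent.

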6.2.3. ORR (Part 2)

ORR, as assessed using RECIST version 1.1 and irRECIST, is a primary efficacy endpoint for Part 2. The following analyses will be performed in the mITT population by tumor type (NSCLC or urothelial carcinoma) and pooled:

1. ORR by visit, separately for RECIST 1.1 and irRECIST: investigator provided tumor response CR, PR, and CR+PR will be presented by descriptive statistics (frequency and percentage) and 95% confidence interval.
2. Best overall response of CR, PR, and CR+PR, separately for RECIST 1.1 and irRECIST. This will include best overall response derivation without confirmation and with confirmation. Descriptive statistics (frequency and percentage) and 95% confidence interval will be provided.

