Anti-tumor activity will be assessed through radiological tumor assessments conducted at baseline, during treatment as specified in the [Schedule Of Activities](#), whenever disease progression is suspected (eg, symptomatic deterioration), and at the time of withdrawal from treatment, if not done in the previous 3 weeks, after end of treatment for patients who did not end treatment due to disease progression, death, or withdrawal of consent, a tumor assessment will be performed every 12 weeks until disease progression by irRECIST, initiation of a new anti-cancer treatment, or end of trial (2 years after LPFD, see [Section 13.2](#)), whichever is first. Note: If a patient is classified as having PD during an on-treatment tumor assessment, then confirmation of PD by a second scan in the absence of rapid clinical deterioration is required per irRECIST.

CT or MRI scans to be done every 6 weeks (± 5 days) for patients on IV administration portion and every 8 weeks (± 5 days) for Parts 1 and 2 SC administration portion from the start of study entry (defined as C1D1) until disease progression by immune-related RECIST (irRECIST), death, withdraw consent, or subsequent administration of an anti-chemotherapy agent. CT or MRI scans may be assessed every 12 weeks (± 5 days) for patients who 1) have remained on treatment for ≥ 24 weeks, and 2) have no confirmed progression by irRECIST within the last 6 months, and 3) have demonstrated stability of disease. Tumor assessments should be fixed according to the calendar, regardless of treatment delays.

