3. ENDPOINTS AND COVARIATES: DEFINITIONS AND CONVENTIONS

3.1. Primary Endpoint(s)

Part 1:

- *DLTs at escalated doses of PF-06801591.* The specific definition of DLT is provided in the study protocol.
- Adverse Events (AEs) as characterized by type, frequency, severity (as graded by National Cancer Institute Common Terminology Criteria for Adverse Events [NCI CTCAE] version 4.03), timing, seriousness, and relationship to study therapy PF-06801591.
- Laboratory abnormalities as characterized by type, frequency, severity (as graded by NCI CTCAE version 4.03), and timing.

Part 2:

- AEs as characterized by type, frequency, severity (as graded by NCI CTCAE version 4.03), timing, seriousness and relationship to study therapy PF-06801591 *administered by SC administration.*
- Laboratory abnormalities as characterized by type, frequency, severity (as graded by NCI CTCAE version 4.03) and timing.
- ORR as assessed using RECIST version 1.1 and irRECIST. ORR is defined as the proportion of patients who achieved completed response (CR) or partial response (PR) per RECIST 1.1, or irRECIST.

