4.2. Safety Analysis Set

The safety analysis set includes all enrolled patients who receive at least one dose of study medication.

4.3. 'PER PROTOCOL' Analysis Set

The per protocol analysis set includes all enrolled patients who received at least one dose of study treatment and who did not have major treatment deviations during the Cycle 1. For the IV administration of PF-06801591, patients with major treatment deviations in the 21-day DLT observation period are not evaluable for the MTD assessment and will be replaced as needed to permit MTD estimation.

For the SC administration of PF-06801591, patients with major treatment deviations in the 28-day observation period will not be evaluable for DLT.

Major treatment deviations include:

- Administration of <50% of the planned dose of PF-06801591, provided that the reduction is not due to toxicity attributable to PF-06801591.
- Administration of >150% of the planned dose of PF-06801591.

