4.6. Modified Intent-to-Treat Set

The modified intent-to-treat (mITT) population is defined as all the randomized subjects who have received at least 1 dose of study medication, have measurable disease baseline assessment (within 28 days prior to study entry) and at least 1 post baseline assessment or disease progression, global deterioration of health status, or death. The mITT population will be used for anti-tumor assessment.

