6. ANALYSES AND SUMMARIES

For efficacy related endpoints in this study, as both RECIST 1.1 and irRECIST will be used for tumor assessments, and there are different requirements in these criteria in terms of confirming tumor response or progression, the following analysis plan will be implemented:

Endpoint	Part 1		Part 2	
	RECIST 1.1	irRECIST	RECIST 1.1	irRECIST
ORR (or irORR)	Unconfirmed	Both	Both	Both
PFS (or irPFS)	Unconfirmed	Both	Unconfirmed*	Both
DOR (or irDOR)	Unconfirmed	Both	Both	Both
DOSD (or irDOSD)	Unconfirmed	Both	Both	Both
TTP	Unconfirmed	Both	Unconfirmed*	Both
TTR	Unconfirmed	Both	Both	Both

Note: “Both” in the above table represents both unconfirmed and confirmed tumor assessments.

*: Confirmation for progressed disease is not applicable in RECIST 1.1

In the “unconfirmed” analyses (i.e. tumor response or progression without confirmation required), all tumor assessments data will be included for analyses. Specifically, regardless if a patient’s tumor response or progression is subsequently confirmed or not, the patient data will all be included in the “unconfirmed” analyses. This is a more comprehensive analysis where tumor confirmation is not required and not taken into account. For example in the ORR analysis, if a patient achieved CR or PR, regardless it is subsequently confirmed or not, the patient will be included in the numerator.

In the “confirmed” analyses (i.e. tumor response or progression with confirmation required), only those tumor assessments data that’s subsequently confirmed by a consecutive tumor scan will be considered as a “success” or “event” and be included for analyses as appropriate. For example, in the ORR analysis, a patient will only be counted in the numerator (the “success”) if the tumor response (CR or PR) is subsequently confirmed. If a patient’s tumor response is not subsequently confirmed, the patient will still be included in the denominator (the population set) but will not be included in the numerator (the “success”). In the PFS analysis, only a PD that’s subsequently confirmed will be considered as an “event”.

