6.3. Analysis for Secondary Endpoints

6.3.1. Efficacy Endpoints Analysis

Except ORR for Part 2, efficacy is a secondary objective. The efficacy analysis will be performed in the mITT population. Part 1 and Part 2 data will be summarized separately, and may also be pooled together for analysis if deemed necessary. Efficacy data assessed by RECIST will be analyzed separately from those assessed by irRECIST.

Tumor response data in Part 1, Part 2 and across the two Parts may be summarized with descriptive statistics (frequency and percentage) in the following groups by visit and then best overall response across all visits:

- Overall summary for all doses and all tumor types;
- By tumor type regardless of dose;
- By dose regardless of tumor type;
- By dose and tumor type if data permit.

Summary tables of best overall response rate, PFS, OS, DOSD, and DOR may be provided by the groups aforementioned when deemed necessary (e.g. if there are ≥ 5 patients in a specific group).

Efficacy listings (tumor measurements listings and tumor response listings) will be provided that include the investigator provided tumor measurement data, tumor response, best overall response, first CR/PR date, last date with CR or PR, most recent date without progression, progression date, death date, and last tumor assessment date, etc.

Swimmer plot for individual clinical response and time on treatment, waterfall plot for individual tumor size percent change from baseline, and spider plot for individual tumor size percent change from baseline over time will be presented for RECIST and irRECIST separately.

The following table provides an overview of the efficacy analysis.

Endpoint	Analysis Set	Statistical Method	Model/ Covariates/ Strata	Missing Data
Overall response	mITT	Exact CI	See aforementioned summary descriptions on data pooling across dose and tumor type	Observed case
Overall Survival	ITT	Kaplan-Meier	See aforementioned summary descriptions on data pooling across dose and tumor type	Censored at last visit
Progression Free Survival (PFS)	mITT	Kaplan-Meier	See aforementioned summary descriptions on data pooling 3721 across dose and tumor type	Censored per Appendix 9.2
Time to Progression (TTP) and Time to Response (TTR)	mITT	Kaplan-Meier	See aforementioned summary descriptions on data pooling across dose and tumor type	Censored per Appendix 9.2

Endpoint	Analysis Set	Statistical Method	Model/ Covariates/ Strata	Missing Data

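### The Part 2 primary ORR is computed only in an mITT set that drops treated patients with no post-baseline scan and no qualifying event, which can only raise the estimate; no all-treated ORR is planned.

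*SAP*

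**What the plan says.** SAP 3.1 sets out the endpoint without limiting it to evaluable patients: "ORR is defined as the proportion of patients who achieved completed response (CR) or partial response (PR) per RECIST 1.1, or irRECIST". The analysis set comes later. SAP 6.2.3 states: "The following analyses will be performed in the mITT population by tumor type (NSCLC or urothelial carcinoma) and pooled". SAP 4.6 builds that set from "all the randomized subjects who have received at least 1 dose of study medication", with a measurable-disease baseline assessment within 28 days before study entry, and then requires "at least 1 post baseline assessment or disease progression, global deterioration of health status, or death". It sets no time limit on the qualifying event.

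The overview table in SAP 6.3.1 again gives overall response to mITT and enters "Observed case" as the missing-data rule, a term the SAP does not define. In the same table only overall survival is assigned to ITT. An all-treated set exists in SAP 4.2: "The safety analysis set includes all enrolled patients who receive at least one dose of study medication". No ORR is assigned to it or to the Full Analysis Set.

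For responses that are not confirmed, SAP 6 says "the patient will still be included in the denominator (the population set) but will not be included in the numerator". SAP 5.5 likewise treats a response as unconfirmed when the pandemic prevented the confirming scan. Neither section covers a patient with no post-baseline scan at all. Protocol 9.1 lists no mITT set, and protocol 9.4 names no analysis set for ORR.

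**The concern.** The first Part 2 scan falls at about week 8, so patients can leave before it. The mITT definition keeps those who progress, deteriorate globally or die. It loses those who withdraw consent, are lost to follow-up or start another therapy before any scan and have none of those events. None of them can have a recorded CR or PR, so their removal acts on the denominator alone.

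Because the qualifying event has no time limit, entry to the set also depends on follow-up. An unscanned patient counts if a later death is recorded and does not count if alive or lost.

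ORR is a Part 2 primary endpoint. The protocol intends Part 2 to show whether efficacy is comparable to approved agents (1.2.7), and confirmation of efficacy and safety would make 300 mg SC the recommended Phase 2 dose (3.1.8). With no hypothesis test, the estimate and its interval are what readers will use, so the denominator should be neither selective nor open to interpretation.

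**Working it through.** **Inputs.** NSCLC n = 70 and urothelial n = 30 (protocol 9.3). Planning ORR 19% (protocol 9.3); the nearest whole count is 13 of 70. Two-sided 95% exact intervals (SAP 5.3.2). The number k of treated patients with no post-baseline assessment and no qualifying event is not given, so it is assumed: 0 to 7 of 70 and 0 to 2 of 30. The urothelial count of 6 responders is also assumed. The SAP still carries 60 and 40 for the cohort sizes; the protocol's current sizes are used here.

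**Reproducing the plan's own figures.** Protocol 9.3 gives an 80% interval of 13.4 to 25.2% and a 90% interval of 12.2 to 27.3% for N = 70. Wilson intervals on 13/70 give 13.4 to 25.2% and 12.1 to 27.3%, which agree to rounding. The precision statement therefore rests on the whole cohort of 70.

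The worked example for the early look also counts everyone. With a Beta(0.235, 1) prior and 4 responders of 30, the posterior is Beta(4.235, 27) and P(ORR > 10%) = 0.69, matching the stated figure of about 70%. If two unscanned patients were removed, Beta(4.235, 25) would give 0.74.

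**Effect of the exclusion.** All-treated ORR = x/n. With k unscanned patients removed, ORR = x/(n-k) = (x/n) × n/(n-k). This is at or above x/n for every k ≥ 0.

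| Cohort | k | x/(n-k) | ORR | Exact 95% CI | n/(n-k) |
|---|---|---|---|---|---|
| NSCLC | 0 | 13/70 | 18.6% | 10.3 to 29.7 | 1.000 |
| NSCLC | 2 | 13/68 | 19.1% | 10.6 to 30.5 | 1.029 |
| NSCLC | 4 | 13/66 | 19.7% | 10.9 to 31.3 | 1.061 |
| NSCLC | 7 | 13/63 | 20.6% | 11.5 to 32.7 | 1.111 |
| Urothelial | 0 | 6/30 | 20.0% | 7.7 to 38.6 | 1.000 |
| Urothelial | 1 | 6/29 | 20.7% | 8.0 to 39.7 | 1.034 |
| Urothelial | 2 | 6/28 | 21.4% | 8.3 to 41.0 | 1.071 |

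The largest NSCLC shift shown is 20.6 - 18.6 = 2.0 points, against an interval width of 29.7 - 10.3 = 19.4 points. The largest urothelial shift shown is 21.4 - 20.0 = 1.4 points.

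**What limits k.** Protocol 7.4 calls for a scan "at the time of withdrawal from treatment, if not done in the previous 3 weeks", and footnote u of the Part 2 Schedule of Activities continues scans every 12 weeks for patients who stop for reasons other than progression, death or consent withdrawal. Most patients who stop for toxicity would therefore still enter mITT. The protection is not complete, because protocol 7.4 and footnote u also ask for the end-of-treatment scan only when more than 8 weeks have passed since the last evaluation. These two timing rules need to be reconciled.

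**The case against.** The strongest opposing case is that the effect is small and mostly visible already. Eligibility requires a status likely to allow at least 8 weeks of treatment, early progressors and deaths stay in the denominator, and survival follow-up to 2 years after the last patient's first dose will bring in some unscanned patients through recorded deaths. Nothing in the documents supports k as high as 7. SAP 6.1 tabulates patient accounting and lists the evaluation groups, with discontinuation reasons, so a reader could recover x/n. There is no hypothesis test, and an endpoint definition that names no analysis set does not contradict a later section that does. On this view a sensitivity analysis would be enough.

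Much of this stands. The shift is small, k = 7 is an upper illustration and not a forecast, and SAP 3.1 and 4.6 can be read together without formal contradiction. The upward direction is certain only for unscanned patients. For treated patients dropped because they lack a measurable baseline assessment the direction is uncertain, although a measurable lesion is an entry criterion and few are expected.

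What does not stand is that disclosure replaces the analysis. The accounting in SAP 6.1 produces no all-treated ORR and no interval for it. The undefined missing-data entry leaves the handling of unscanned patients to be settled at the analysis stage.

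**Conclusion.** The concern holds and should be fixed. The only analysis set specified for the Part 2 primary ORR removes treated patients who have no post-baseline assessment and no progression, deterioration or death. For those patients the bias is upward by arithmetic. Its size is 0 to about 2 percentage points for NSCLC if 0 to 7 of 70 are lost, and 0 to about 1.4 points for urothelial carcinoma if 0 to 2 of 30 are lost. These figures rest on assumed values of k, 13 NSCLC responders taken from the 19% planning rate, and an assumed 6 urothelial responders. No formal decision depends on the difference; the reported estimate and its exact interval do.

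**What to change.** In SAP 6.2.3 and 6.3.1:

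- Make all treated Part 2 patients in each tumour cohort the population for the primary ORR, using the Safety Analysis Set of SAP 4.2.
- State that patients with no evaluable post-baseline assessment count as non-responders, and put this rule in the efficacy table in place of "Observed case".
- Keep mITT as a supportive analysis, and report the number of treated patients it excludes, with reasons.
- When SAP 4.6 is revised, delete the reference to randomisation, since nobody in this study is randomised. This is editorial and does not affect ORR.

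The cost is SAP wording and one extra denominator, using data already collected. The reported ORR may come out slightly lower.
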